## 11.4. Appendix 4: Study Periods and Treatment Phases

### 11.4.1. Study Periods

The reporting of the study will be divided into three distinct periods, with displays reflecting data collected within each period separately:

- Period 1: Parts A/B – variable and fixed run-in periods combined, receiving open-label mepolizumab treatment
- Period 2: Part C – double-blind treatment period, receiving mepolizumab or placebo
- Period 3: Part D – optional treatment switch period, returning to open-label mepolizumab treatment

Data will be collected across all periods within a single study database and will be attributed to an individual period according to the time of occurrence/assessment relative to the attendance of subjects at specific visits as follows:

Study Period	Period Start	Period End
Period 1: Parts A/B	Date of Pre-screening visit	Subjects who are randomized and receive double-blind treatment: Day prior to Period 2 (Part C) start Subjects who are not randomized: Date of study conclusion (screen/run-in failure)
Period 2: Parts C	Date of first dose within Part C (Visit C1)	Subjects completing study Part C: Date of study conclusion Subjects discontinuing study treatment/withdrawing early from within Part C: Latest date of 1) Part C Early Withdrawal visit and 2) study conclusion Subjects who switch to study Part D: Day prior to Period 3 (Part D) start
Period 3: Parts D	Date of first dose within Part D	Subjects completing study Part D: Date of study conclusion Subjects discontinuing study treatment/withdrawing early from within Part D: Latest date of 1) Part D Early Withdrawal visit and 2) study conclusion

**11.4.2. Treatment Phases (Exacerbations and Healthcare Resource Use)**

Exacerbations and healthcare resource use will be classified into treatment phases according to the time of occurrence/assessment relative to the dates of the study treatment and/or the participation of subjects within specific study parts (as dictated by attendance at specific visits) as shown in the table below:

Treatment Phase	Definition
Pre-treatment	Onset Date & time < First dose of open-label mepolizumab
On-treatment (Parts A/B)	Subjects who are randomized and receive double-blind treatment: First dose of open-label mepolizumab ≤ Onset Date & time < First dose of double-blind treatment Subjects who are not randomized: First dose of open-label mepolizumab ≤ Onset Date & time ≤ Earliest of (1) Last dose of open-label mepolizumab + 28 days or (2) Early Withdrawal visit date 
Post-treatment (Parts A/B)	Subjects who are not randomized: Onset Date & time > Earliest of (1) Last dose of open-label mepolizumab + 28 days or (2) Early Withdrawal visit date 
On-treatment (Part C)	Subjects completing study Part C: First dose of double-blind treatment ≤ Onset Date & time ≤ C14 (Exit Visit) visit date Subjects discontinuing study treatment/withdrawing early from within Part C: First dose of double-blind treatment ≤ Onset Date & time ≤ Earliest of (1) Last dose of double-blind treatment + 28 days or (2) Early Withdrawal / IP Discontinuation visit date Subjects who switch to study Part D: First dose of double-blind treatment ≤ Onset Date & time < First dose of open-label mepolizumab within Part D
Post-treatment (Part C)	Subjects completing study Part C: Onset Date & time > C14 (Exit Visit) visit date Subjects discontinuing study treatment/withdrawing early from within Part C: Onset Date & time > Earliest of (1) Last dose of double-blind treatment + 28 days or (2) Early Withdrawal / IP Discontinuation visit date
On-treatment (Part D)	Subjects completing study Part D: First dose of open-label mepolizumab within Part D ≤ Onset Date & time ≤ D14 (Exit Visit) visit date Subjects discontinuing study treatment/withdrawing early from within Part D: First dose of open-label mepolizumab within Part D ≤ Onset Date & time ≤ Earliest of (1) Last dose of open-label mepolizumab within Part D + 28 days or (2) Early Withdrawal / IP Discontinuation visit date
Post-treatment (Part D)	Subjects completing study Part D: Onset Date & time > D14 (Exit Visit) visit date Subjects discontinuing study treatment/withdrawing early from within Part D: Onset Date & time > Earliest of (1) Last dose of open-label mepolizumab within Part D + 28 days or (2) Early Withdrawal / IP Discontinuation visit date

[1] Note subjects who are deemed not eligible for randomization at visit C1 will perform their Early Withdrawal visit and associated assessments at this visit.

Time of study treatment dosing and start/stop time of assessment should be considered, if collected.

Where the assessment occurs on the date of study treatment and time is not available, assessment assumed to have occurred following dosing.

Refer to [Appendix 7: Reporting Standards for Missing Data](#) for handling of missing and partial dates in exacerbations.

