All subjects will be given a paper diary starting at Visit 1 through the Exit Visit or EW to record any medical problems experienced during the study, and any medication taken for those medical problems. Any unscheduled healthcare resource utilization (e.g.; physician visits, emergency department visits) due to asthma will also be recorded.

Subjects will complete a daily electronic diary (eDiary) during the fixed run-in Part B, double-blind treatment period Part C and open-label Part D. Subjects will be asked to provide the following information daily:

- AM Peak flow before rescue medication usage (L/min)
- Rescue medication use
- Nocturnal awakening due to asthma symptoms requiring rescue medication use
- Asthma symptoms
- Missed days of work/school due to asthma

Subjects will also be asked to provide the following information via eDiary weekly:

- Asthma Control Questionnaire-5 (ACQ-5)

Part D: Optional Switch to Open-Label Mepolizumab

Subjects who experience a clinically significant asthma exacerbation during the double-blind treatment period Part C will require a prompt assessment by the investigator to determine if they should continue taking double-blind study treatment.

Subjects deemed to be unsuitable to continue double-blind study treatment by the investigator should discontinue double-blind investigational product (IP) and complete a Discontinuation of IP Visit approximately 4 weeks following their last dose of double-blind IP.

Subjects discontinuing IP due to a clinically significant asthma exacerbation are eligible to enter optional Part D of the study and receive open-label mepolizumab in addition to their standard of care therapy for the remainder of the study, through Part D, to Visit D13. Subjects switching to Part D should complete the Discontinuation of IP Visit and their first Part D visit on the same day, corresponding to the week post-randomization. No assessments should be duplicated.

Switch to Part D between visits: For example, if a subject completed Visit C7 at Week 24 (and the subject received a dose of IP at Visit C7) and it is later determined that they should switch to Part D, the IP Discontinuation assessments and the first visit in Part D will be D8 at Week 28.

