Switch to Part D during a visit: If a subject is in the process of completing a Part C visit, as long as they have not yet received a dose of IP, they may be switched to Part D at that same visit (e.g., a subject that is part way through Visit C7 at Week 24 and whose last dose of IP was at Visit C6, Week 20 can be switched to Part D and complete the IP Discontinuation assessments and Visit D7 at that same visit, Week 24).

Haematology samples will be collected for each of the subject's first 3 visits of Part D, and then according to designated Visits in [Table 8](#).

An Exit Visit will be conducted 52 weeks after randomization (whether the subject is in Part C or Part D) in order to assess subject's efficacy parameters, immunogenicity status, and to conduct additional safety assessments.

Subjects who permanently discontinue study treatment in Part C or D of the study are NOT required to withdraw from the study. If a subject discontinues double blind study treatment during Part C and does not switch to Part D at their next visit (IP Discontinuation Visit) after experiencing a clinically significant asthma exacerbation, the subject cannot enter Part D at a later visit.

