Pregnancy Test ⁵	U	U	U	U	U	U	U	U	U	U	U	U	U	U	U
Immunogenicity														X	X
Efficacy Assessments³															
Exacerbation review	X	X	X	X	X	X	X	X	X	X	X	X	X	X	X
Spirometry				X			X			X				X	X
Worksheets/Diary/IP/ eCRF³															
Administer open-label mepolizumab	X	X	X	X	X	X	X	X	X	X	X	X	X	X	
Dispense albuterol/salbutamol	X	X	X	X	X	X	X	X	X	X	X	X	X	X	
Collect albuterol/salbutamol	X	X	X	X	X	X	X	X	X	X	X	X	X	X	X
Dispense paper diary	X	X	X	X	X	X	X	X	X	X	X	X	X	X	
Review eDiary ⁶ (symptoms, rescue use, nocturnal awakenings, PEF, ACQ-5, missed days of work/school)	X	X	X	X	X	X	X	X	X	X	X	X	X	X	X
Collect eDiary														X	X ⁷

PART D Procedures	OPTIONAL Open-Label Switch to mepolizumab Part D ¹ (window is ± 1 week)														IPDISC/EW Visit ⁸		
	Visit	D1	D2	D3	D4	D5	D6	D7	D8	D9	D10	D11	D12	D13		Exit Visit	
Week of Study²	0	4	8	12	16	20	24	28	32	36	40	44	48	52			
Collect/review paper diary	X	X	X	X	X	X	X	X	X	X	X	X	X	X	X	X	
Contact IRT															X	X	
Complete eCRF	X	X	X	X	X	X	X	X	X	X	X	X	X	X	X	X	X

1. The combined treatment period (Part C) and any switch to open-label mepolizumab (Part D) should not exceed a total duration of 52 weeks.
2. Subjects may enter the Open-label Switch Part D at any point during Part C provided they meet switch criteria, starting with the week of study that the switch is made and continuing until week 52, discontinuation of IP or early withdrawal.
3. All assessments to be completed prior to dosing
4. Haematology samples will be collected for each of the subject's first 3 visits of Part D, and then according to designated Visits in [Table 8](#)
5. Urine pregnancy tests (U) should be conducted every 4 weeks for women of child bearing potential.
6. The eDiary should be reviewed at each visit. Weekly review is not required in Part D.
7. The eDiary is only collected at an Early Withdrawal or Exit visit.
8. IPDISC/EW visit should be conducted 4 ± 1 weeks from the subject's last dose

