#### 7.1.4. Strategy for Intercurrent (Post-Randomization) Events

A hypothetical estimand strategy will be applied in the handling of the intercurrent event of discontinuation of double-blind treatment. The treatment effect therefore refers to the outcome if all patients had continued to take double-blind treatment.

Only the On-treatment (Part C) period will be used in the analysis and subjects will be analysed according to the treatment each subject received for more than 50% of injections within Part C (see Section 5.1).

All subjects will be considered to be at risk from their first dose of double-blind treatment at visit C1. Subjects who complete Part C will be considered to be at risk up to their Week 52 (Exit Visit/C14) visit date. Subjects who discontinued double-blind treatment prior to experiencing an exacerbation (event) will be censored at the time of treatment discontinuation [see On-treatment (Part C) definition within Section 11.4.2].

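### An untimed exacerbation dated on the first Part D dose date falls in Part D, so a first event that triggered a same-visit switch is censored in the primary analysis

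*SAP*

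**What the plan says.** SAP 11.4.2 assigns exacerbations and healthcare resource use to treatment phases. For subjects who switch, the Part C on-treatment phase is "First dose of double-blind treatment ≤ Onset Date & time < First dose of open-label mepolizumab within Part D", and the Part D phase begins at that dose, inclusive. Recorded times take priority: "Time of study treatment dosing and start/stop time of assessment should be considered, if collected". Without them the default is "Where the assessment occurs on the date of study treatment and time is not available, assessment assumed to have occurred following dosing".

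SAP 7.1.4 uses only the Part C on-treatment phase for the primary endpoint and adds: "Subjects who discontinued double-blind treatment prior to experiencing an exacerbation (event) will be censored at the time of treatment discontinuation". SAP 7.2.2.1 applies the same classification to time to first exacerbation requiring hospitalization or an ED visit.

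Protocol 5.1 makes the exacerbation the route into Part D: "Subjects discontinuing IP due to a clinically significant asthma exacerbation are eligible to enter optional Part D of the study". It also permits a switch during a visit: "as long as they have not yet received a dose of IP, they may be switched to Part D at that same visit". Footnote 3 of protocol Table 8, which covers the exacerbation review in Part D, reads "All assessments to be completed prior to dosing".

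**The concern.** The default assumes an order of events that the protocol rules out in one situation. If an exacerbation led to a switch at the same visit, it was known before any product was given that day. Placing it after the dose reverses cause and effect: the event that ended double-blind treatment is recorded as having happened under open-label treatment.

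When that event is the subject's first in Part C, a true primary event becomes a censored observation. The subject is censored because of the event, so the censoring is informative. It can happen only to subjects who switch. At stake are a few events in the primary analysis, the matching Kaplan-Meier probabilities, and the hospitalization/ED endpoint, which inherits the same rule.

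**Working it through.** **Rule trace.** Take a same-visit switch at Week 24, with the first Part D dose on Part C day 169 (24 × 7 + 1).

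| Onset | Phase under 11.4.2 | Primary analysis |
|---|---|---|
| Day 168 | Part C | counted |
| Day 169, timed before the dose | Part C | counted |
| Day 169, no usable time | Part D | censored if no earlier event |

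**Comparison within the SAP.**
- A subject who stops product without entering Part D stays on-treatment, under 11.4.2, up to and including the earlier of last dose + 28 days and the IP Discontinuation visit date. An onset on that visit date, within 28 days of the last dose, is counted. Switchers complete the same discontinuation visit on the day of their first Part D visit, yet an untimed onset that day is not counted.
- SAP 11.4.3 treats untimed visit-based and eDiary data on a dosing date as preceding the dose. Diary data from the switch day can therefore be Part C while the exacerbation is Part D.

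**The plan's own power figure.** Inputs from protocol 10.2.1 and 10.1: 150 per arm, 40% events on mepolizumab, 60.5% on placebo, 20% withdrawing before an event, true HR 0.55, two-sided 5%.
- Placebo proportion: 1 − 0.60^(1/0.55) = 60.5%, as stated.
- Planned events: 0.8 × 150 × (0.40 + 0.605) = 120.6, assuming the 20% contribute no event.
- Schoenfeld power: Φ(√120.6/2 × |ln 0.55| − 1.96) = 90.7%, against 90% stated.
- Freedman power: Φ(√120.6 × 0.45/1.55 − 1.96) = 89.0%.

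**Size of the effect.** The documents do not give the number affected, so the share lost is an assumption, shown over a range. The 1/28 row takes onset as uniform over a 28-day dosing interval. It also takes every visit-day onset as untimed, first, qualifying and switched at that visit. The last row is a fixed count, for scale.

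| Share lost | Events lost | Events left | Schoenfeld | Freedman |
|---|---|---|---|---|
| 0 | 0 | 120.6 | 90.7% | 89.0% |
| 1/112 | 1.1 | 119.5 | 90.5% | 88.8% |
| 1/56 | 2.2 | 118.4 | 90.2% | 88.5% |
| 1/28 | 4.3 | 116.3 | 89.7% | 87.9% |
| – | 8 | 112.6 | 88.7% | – |

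**Hazard ratio and event probabilities.** With constant hazards, censoring a share s of events at the moment they occur gives an observed hazard of (1 − s)λ. With s = 1/28 in both arms:
- HR = 0.55 × (27/28)/(27/28) = 0.55.
- Placebo at 52 weeks: 1 − exp(ln 0.395 × 27/28) = 59.2%, from 60.5%.
- Mepolizumab: 1 − exp(0.55 × ln 0.395 × 27/28) = 38.9%, from 40.0%.

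**The case against.** The strongest reply is that the situation is rare. A clinically significant exacerbation needs at least 3 days of IV or oral steroid (doubled for subjects on maintenance), a single IM dose, hospitalisation or an ED visit. An onset dated on the visit day cannot already have 3 days of steroid behind it. It qualifies that day only through an IM dose, ED visit or hospitalisation; otherwise the investigator must have switched the subject on a course just started. This stands, and it makes 1/28 an extreme figure.

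Second, the default is only a fallback. 11.4.2 is written in terms of onset date and time, and if both onset and dosing times were recorded it never applies. The documents leave this open: 11.6.3 and 11.7.2.1 describe exacerbation starts only as dates, and the eCRF is not available. This also stands.

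Third, the drop of 1.0 point at 1/28 is smaller than the 1.7 points between Schoenfeld and Freedman. It is about the same as the 0.9 points between 90.7% and the 89.8% obtained by interpolating protocol Table 10 at 60.5% (89.5% + 0.1 × 2.6). This stands too.

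Fourth, the after-dosing default is a consistent convention for event data, also used in 11.4.4, and Listing 14 would show affected cases by phase. Consistency does not make it right at the switch, and a listing does not change the primary event status.

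Three stronger readings are tempting but unsupported.
- A reader might infer that the plan drops switch-triggering exacerbations in general. It does not: a trigger with an earlier onset date is counted, including one merged with an exacerbation that began less than 7 days before.
- A reader might infer bias in the hazard ratio. That needs an unequal share lost between arms, and the documents give no reason to expect it.
- A reader might take the roughly 120 subjects in protocol 5.3 as confirming about 4 affected switchers. Those are subjects expected to meet the switch criteria, not subjects who switch, and the figure essentially restates the 120.6 planned events.

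**Conclusion.** The rule holds as traced. For a same-visit switch, the default in 11.4.2 gives the wrong phase to an untimed triggering exacerbation dated that day, and 7.1.4 then censors a first event that occurred on double-blind treatment. It also treats switchers differently from other subjects who discontinue, on an equivalent date.

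The consequence is small and may be nil. It requires a missing onset or dosing time, an onset dated on the visit day, a first Part C event, and either qualification that day or a switch on a steroid course just started. At the extreme 1/28 share, about 4.3 events and 1.0 point of power are lost. That share rests on uniform onset dates; if dates cluster on clinic days the count could be higher, at roughly 0.2 points of power per event. The hazard ratio is unchanged under equal shares. Severity is minor, and the reason to act is that the correction is cheap.

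**What to change.** In SAP 11.4.2, for subjects who switch, classify an untimed exacerbation dated on the first Part D dose date, and the healthcare resource use linked to it, as Part C on-treatment. Keep using recorded times where they exist. Keep the after-dosing rule at Visit C1, where it correctly places same-day onsets in Part C.

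Matching edits:
- 11.6.1: define the Part C study day for these events on that date, since for switchers it now stops before the first Part D dose.
- 11.4.1: leave the period boundary as it is, with a one-line exception for these events.
- 11.4.4: state how the same exacerbation is classified if it is also reported as an SAE, because that section keeps its own after-dosing rule.

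List any affected subjects before unblinding.

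The cost is these SAP edits, matching changes to the exacerbation, resource-use and time-to-event derivations, and one blinded listing. No new data are collected. The downside is that an untimed new event that truly began after the Part D dose that day would be counted in Part C. This should rarely matter, because a switcher should already have had a qualifying event.

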**11.4.3. Treatment Phases (Visit Based Efficacy and Safety Data)**

Visit based efficacy data, safety data and eDiary data will be classified into treatment phases according to the time of occurrence/assessment relative to the dates of the study treatment and/or the participation of subjects within specific study parts (as dictated by attendance at specific visits) as shown in the table below:

Treatment Phase	Definition
Pre-treatment	Date & time $\leq$ First dose of open-label mepolizumab
On-treatment (Parts A/B)	Subjects who are randomized and receive double-blind treatment: First dose of open-label mepolizumab < Date & time $\leq$ First dose of double-blind treatment Subjects who are not randomized: First dose of open-label mepolizumab < Date & time $\leq$ Earliest of (1) Last dose of open-label mepolizumab + 28 days or (2) Early Withdrawal visit date 
Post-treatment (Parts A/B)	Subjects who are not randomized: Date & time > Earliest of (1) Last dose of open-label mepolizumab + 28 days or (2) Early Withdrawal visit date 
On-treatment (Part C)	Subjects completing study Part C: First dose of double-blind treatment < Date & time $\leq$ C14 (Exit Visit) visit date Subjects discontinuing study treatment/withdrawing early from within Part C: First dose of double-blind treatment < Date & time $\leq$ Earliest of (1) Last dose of double-blind treatment + 28 days or (2) Early Withdrawal / IP Discontinuation visit date Subjects who switch to study Part D: First dose of double-blind treatment < Date & time $\leq$ First dose of open-label mepolizumab within Part D
Post-treatment (Part C)	Subjects completing study Part C: Date & time > C14 (Exit Visit) visit date Subjects discontinuing study treatment/withdrawing early from within Part C: Date & time > Earliest of (1) Last dose of double-blind treatment + 28 days or (2) Early Withdrawal / IP Discontinuation visit date
On-treatment (Part D)	Subjects completing study Part D: First dose of open-label mepolizumab within Part D < Date & time $\leq$ D14 (Exit Visit) visit date Subjects discontinuing study treatment/withdrawing early from within Part D: First dose of open-label mepolizumab within Part D < Date & time $\leq$ Earliest of (1) Last dose of open-label mepolizumab within Part D + 28 days or (2) Early Withdrawal / IP Discontinuation visit date
Post-treatment (Part D)	Subjects completing study Part D: Date & time > D14 (Exit Visit) visit date Subjects discontinuing study treatment/withdrawing early from within Part D: Date & time > Earliest of (1) Last dose of open-label mepolizumab within Part D + 28 days or (2) Early Withdrawal / IP Discontinuation visit date

[1] Note subjects who are deemed not eligible for randomization at visit C1 will perform their Early Withdrawal visit and associated assessments at this visit.

Time of study treatment dosing and start/stop time of assessment should be considered, if collected.

Where the assessment occurs on the date of study treatment and time is not available, assessment assumed to have been performed prior to dosing.

Data classified in this manner will include questionnaires, lung function, laboratory assessments, liver events, immunogenicity, ECGs, vital signs and diary data.

#### 11.4.4. Treatment Phases (Adverse Events and Cardiovascular Events)

Adverse events and cardiovascular events will be classified into treatment phases according to the time of occurrence relative to the dates of study treatment within specific study parts as shown in the table below:

Treatment Phase	Definition
Pre-treatment	Onset Date & time < First dose of open-label mepolizumab If mepolizumab treatment is never started, then all will be classified as pre-treatment.
On-treatment (Parts A/B)	Subjects who are randomized and receive double-blind treatment: First dose of open-label mepolizumab ≤ Onset Date & time < First dose of double-blind treatment Subjects who are not randomized: First dose of open-label mepolizumab ≤ Onset Date & time ≤ Last dose of open-label mepolizumab + 28 days
Post-treatment (Parts A/B)	Subjects who are not randomized: Onset Date & time > Last dose of open-label mepolizumab + 28 days
On-treatment (Part C)	Subjects who switch to study Part D: First dose of double-blind treatment ≤ Onset Date & time < First dose of open-label mepolizumab within Part D All other Part C Subjects: First dose of double-blind treatment ≤ Onset Date & time ≤ Last dose of double-blind treatment + 28 days
Post-treatment (Part C)	Subjects who do not switch to study Part D: Onset Date & time > Last dose of double-blind treatment + 28 days
On-treatment (Part D)	First dose of open-label mepolizumab within Part D ≤ Onset Date & time ≤ Last dose of open-label mepolizumab within Part D + 28 days
Post-treatment (Part D)	Onset Date & time > Last dose of open-label mepolizumab within Part D + 28 days

Time of study treatment dosing and start/stop time of event should be considered, if collected.

Where the event onset occurs on the date of study treatment and time is not available, event assumed to have occurred following dosing.

If an AE start date is missing or partial then the AE will be considered on-treatment unless there is evidence to the contrary (e.g. month/year of onset date is present and is earlier than the month/year of first dose of treatment).

Refer to [Appendix 7: Reporting Standards for Missing Data](#) for handling of missing and partial dates in adverse events and cardiovascular events.

